**b. End Points – Safety**

There is a potential risk of breach of confidentiality. However, all research data will be kept in a password protected personal computer and identifiers will be kept separately. Access to the data will only be kept within the study team, including the PI and the Co-investigators.

There is a potential risk that patients under the intervention arm may have a higher incidence of 30-day or 60-day MACE, as the hypothesis is that more patients will choose to be discharged rather than be admitted to the ED observation unit, which may lead to a delay in further cardiac testing and definitive management. However, this is unlikely as the study includes only patients with a low overall risk of MACE (0.9-1.7%) who are not likely to require any cardiac intervention.

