### **3.5. Withdrawal Criteria**

The study may be continued if the intervention has been shown to be associated with an increase in 30- or 60-day MACE as compared to the control arm.

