## **7. SAFETY MEASUREMENTS**

### **7.1. Definitions**

Serious adverse events are defined as either 30-day or 60-day MACE. If there is an increase in 30-day or 60-day MACE amongst subjects in the intervention arm during interim analysis at 50% of our recruitment target, the PI will be responsible for reporting this to the DSRB.

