### **7.3. Safety Monitoring Plan**

The PI and study team will perform data and safety monitoring. The data will be reviewed on a quarterly basis and both adverse and serious adverse events such as 30- and 60-day major adverse cardiac events will be monitored. The principal investigator will review the study data on a quarterly basis for completeness. Data integrity will be assured by the means of doing spot checks on the data collected and comparison with the patient's electronic records. The study will be stopped based on safety if it is shown that there is an increase in 30- or 60-day MACE for patients in the intervention arm. The dissemination of data and safety information will be done by the principal investigator via face-to-face contact and e-mail if necessary.

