### **9.2. Statistical and Analytical Plans**

Intention-to-treat analysis will be carried out; proportions will be evaluated using chi-square tests, non-parametric variables with Mann-Whitney *U* and parametric variables with Student's *t* tests as appropriate.

An interim analysis will be done when 50% of recruitment has been reached to check for incidence of adverse outcomes such as 30-day or 60-day MACE. If there is a significant increase in 30-day or 60-day MACE in the intervention arm as compared to the control arm, the study will be stopped.

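### Sections 3.5, 7.3 and 9.2 contradict each other on what excess MACE in the intervention arm does to the trial: one lets it continue, two stop it, on differently worded triggers

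*Combined protocol and SAP*

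**What the plan says.** Four sections say what follows from more MACE in the CPC arm than under usual care.

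- Section 3.5 (Withdrawal Criteria): "The study may be continued if the intervention has been shown to be associated with an increase in 30- or 60-day MACE".
- Section 7.3 (Safety Monitoring Plan): "The study will be stopped based on safety if it is shown that there is an increase in 30- or 60-day MACE". The same section sets up periodic review: "The data will be reviewed on a quarterly basis and both adverse and serious adverse events" are to be monitored. The stopping sentence is not tied to any particular look.
- Section 9.2 (Statistical and Analytical Plans): "An interim analysis will be done when 50% of recruitment has been reached". If that look finds "a significant increase in 30-day or 60-day MACE in the intervention arm as compared to the control arm, the study will be stopped".
- Section 7.1 (Definitions): if MACE is increased in the intervention arm "during interim analysis at 50% of our recruitment target, the PI will be responsible for reporting this to the DSRB". Stopping is not mentioned.

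The only test named for such a comparison is the general statement in Section 9.2 that "proportions will be evaluated using chi-square tests". The only significance level in the plan is the two-sided 0.05 in Section 9.1, which belongs to the sample size for observation-unit admissions.

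**The concern.** Excess MACE in the CPC arm is the clinical risk that the protocol itself names. Section 2.4.b says: "There is a potential risk that patients under the intervention arm may have a higher incidence of 30-day or 60-day MACE". The rule for acting on it should be readable in one way only. As written, the same finding lets the trial continue under Section 3.5 and stops it under Sections 7.3 and 9.2. Those two agree on the consequence but word the trigger differently: an increase that is shown, or one that is significant.

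Section 7.3 gives the monitoring to the investigator and study team, who are unblinded (Section 6.1). A rule left open would therefore be interpreted by people who can already see the results by arm. With about one expected event per arm or fewer, the choice between the two triggers largely decides what happens.

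**Working it through.** **1. The rules side by side**

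| Section | Trigger | Look | Consequence |
|---|---|---|---|
| 3.5 | association with an increase has been shown | not stated | may be continued |
| 7.3 | an increase is shown | not stated; section describes quarterly review | will be stopped |
| 9.2 | significant increase, no level stated | 50% interim | will be stopped |
| 7.1 | increase | 50% interim | report to the review board (DSRB) |

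There are two opposed consequences for the trial, and two trigger wordings for stopping it. The Section 7.1 report can coexist with any of them.

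**2. Inputs for the size of the trigger problem**

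- 6-week MACE risk p = 0.9-1.7% (Section 1.2.b).
- Patients per arm at the interim: 164/2/2 = 41 (Sections 3.6 and 9.1) or 200/2/2 = 50 (Section 3.1).
- Assumed: equal arms, full follow-up, one look, one endpoint, and two-sided p<0.05 where significance is meant.
- Day-30 and day-60 risks, assuming constant hazard, are 1-(1-p)^(d/42). Day 30: 0.64-1.22%. Day 60: 1.28-2.42%.

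Expected events per arm at the 6-week risk run from 41 x 0.009 = 0.37 to 50 x 0.017 = 0.85. At the day-60 risk they run from 0.53 to 1.21.

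**3. Formula**

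Let X be events in the CPC arm and Y events under usual care, each binomial with n per arm. The stopping probability is the sum of P(X=x)P(Y=y) over all tables that meet the trigger:

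- any excess: x > y;
- significance: x > y and two-sided p<0.05.

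With 50 per arm and 4 v 0 events, uncorrected chi-square is 100 x (4 x 50 - 46 x 0)^2 / (50 x 50 x 4 x 96) = 4.17, p = 0.041. At 3 v 0, p = 0.079. So 4 v 0 is the smallest significant table. With continuity correction or Fisher's test it is 6 v 0. The same thresholds hold at 41 per arm.

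**4. Results (exact enumeration, 41-50 per arm)**

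| Trigger and truth | 6-week risk | Day-60 risk |
|---|---|---|
| Any excess, no true harm | 22.8-33.0% | 27.4-36.2% |
| p<0.05 uncorrected, no true harm | 0.035-0.44% | 0.11-0.97% |
| p<0.05 uncorrected, MACE doubled | 0.43-3.87% | at most 6.95% |
| p<0.05 continuity-corrected or Fisher, MACE doubled | 0.006-0.30% | at most 1.07% |

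At the day-30 risk, any excess with no true harm occurs in 18.4-29.2%.

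**5. Follow-up at the interim (secondary)**

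The look is triggered by recruitment, while both MACE endpoints are collected at a 60-day review (Sections 4 and 6.2.c).

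- With uniform accrual over 12 months and an immediate data cut, 164/365.25 x 60 = 26.9 of 82, or 200/365.25 x 60 = 32.9 of 100, lack day 60. That is about one third.
- The Section 4 chart, as far as it can be read, shows an analysis block in February-March 2019. Suppose that this is the interim and data are cut at the end of March. With recruitment from August 2018 to August 2019 (396 days), the midpoint is mid-February and the lag is 44 days. Then (60-44) x 164/396 = 6.6 of 82, about 8%, lack day 60.

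**The case against.** The strongest reply is that this is loose drafting around one intended rule. Under a heading on withdrawal criteria, permission to continue makes no sense, so Section 3.5 probably meant discontinued. Section 9.2 is the statistical section, and it is natural to read its word 'significant' as defining 'shown' in Section 7.3. The 0.05 in Section 9.1 is an obvious default. Other safeguards run in parallel: local deaths are reported within 24 hours (Section 7.2), an increase at the interim goes to the DSRB (Section 7.1), and MACE is reviewed quarterly (Section 7.3).

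Much of this stands. A reader might infer that the sponsor means to carry on despite harm; the documents do not support that, given Sections 7.3 and 9.2. A reader might also infer that a harmless intervention will stop the trial up to a third of the time. That figure needs 'shown' to mean any numerical excess, which no stopping section says and which is not the likeliest reading. Nor do the documents establish that a third of patients will lack follow-up at the interim, since Section 9.2 sets no date for the data cut.

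What does not fall away is the text itself. Even corrected, may be discontinued would differ from will be stopped. No section equates the two triggers, sets a level for the interim, or says whether the Section 7.3 rule applies at quarterly reviews. None of the other safeguards says which comparison stops the trial.

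**Conclusion.** The contradiction is in the current text and must be resolved, because it concerns the decision rule for the trial's own named risk. It consists of two opposed consequences and two differently worded stopping triggers. It is not three different consequences, since Sections 7.3 and 9.2 both stop the trial.

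The wording is not a detail. On the assumptions above, moving from any excess to p<0.05 changes the false-stop probability from 23-33% to under 0.5% at the 6-week risk, and from 27-36% to under 1% at the day-60 risk. Under p<0.05 a true doubling of MACE stops the trial in at most 3.9% (uncorrected) or 0.3% (continuity-corrected) at the 6-week risk, and at most 7.0% or 1.1% at the day-60 risk. These figures depend on the assumed level, a single look, full follow-up and, for day 60, constant hazard. Repeated quarterly looks are not included.

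The base for 50% (200 or 164) and the handling of patients short of day 60 are points to clarify, not errors. Between about 8% and one third could lack day 60, depending on accrual and the data cut.

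**What to change.** Reconcile Sections 3.5, 7.3 and 9.2, and align Section 7.1, into one rule that uses the same trigger wording throughout. State whether it applies at the interim only or also at quarterly reviews. If the trigger is statistical, state the test, level and sidedness. Which rule to adopt is for the sponsor to decide.

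Report the chosen rule's false-stop and detection probabilities on the day-30 and day-60 risks. If it rests on significance, acknowledge that it has very little ability to detect doubled MACE at this size.

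As secondary clarifications, say whether 50% refers to 200 or 164, and how patients short of day 60 are handled at the interim. Restricting the comparison to patients who have reached day 60 would leave out events already known in the others, so that choice is also the sponsor's.

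The cost is wording in four sections and a short calculation. The reconciliation itself needs no change to sample size or data collection.

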## **10. ETHICAL CONSIDERATIONS**

### **10.1. Informed Consent**

Informed consent will be taken after initial assessment and stabilization by the primary physician, and only after initial serum troponin and ECG results are released. If found suitable for the study, the patients will first be approached by their own treating physicians to participate in the project during their visit to the emergency department for consent to be referred to the study team. The investigators of the study will then obtain consent from the patients for the study.

The study team may also recruit patients where the attending physician is part of the study team, and the participant may share a dependent relationship with the study team. In order to prevent coercion or undue influence, participation is voluntary and the research participants may withdraw from the study at any time without any compromise in their medical care. For participants who are patients of the study team, their decision to participate in the research study will not affect the standard of care provided to them. Where possible, the informed consent process will be conducted by a qualified study team member, delegated by the PI, who is not involved in the primary care for the research participant.

The research participants will be recruited by face-to-face contact when they are in the emergency department. The subject will have sufficient time to consider his/her participation in the study, and have the option of discussing their participation with family members if needed. The consent process will take place in the emergency department within the patient's cubicle. There will be privacy to the patient and a non-threatening, quiet environment for the patient to assess the risks and benefits afforded to him/her with participation of the study. In situations where there is a dependent patient-doctor relationship, it would be emphasised that participation is entirely voluntary and there will be no negative consequences from possible refusal or withdrawal from the study. They will also be given ample time to read through the patient information sheet and decide without any influence or coercion.

The PI and co-investigators will obtain consent from the subjects. A team log will be kept to identify the members as well as their responsibilities within the study. There will not be recruitment of non-English speakers, children, illiterate or non-writing individuals, as the study precludes that only English-literate subjects aged 21 years and above will be able to be recruited. Appendix 3 includes the informed consent form that will be used during the study.

### **10.2. IRB review**

The study team will provide for the review and approval of this protocol and the associated informed consent documents by the IRB / NHG DSRB.

### **10.3. Confidentiality of Data and Patient Records**

Research data will be coded, and links between the subjects' identifiers and the codes will be stored on a separately from the research data. Hardcopy data will be stored in a locked cabinet in the PI's office, accessible to authorized study personnel only. Electronic data will be stored on in a secured computer that is password-protected. The databases will not contain subject identifiers and the data linking subject identifiers and the subject identification codes will be stored separately. Research data will not be released to individuals or entities outside the

institution.

## **11. PUBLICATIONS**

If the results of this study are published, they will be credited to members of the study team if they have made significant contributions to the study design, execution and manuscript writing/editing.

## **12. RETENTION OF TRIAL DOCUMENTS**

Records for all participants, including CRFs, all source documentation (containing evidence to study eligibility, history and physical findings, laboratory data, results of consultations, etc.) as well as IRB records and other regulatory documentation will be retained by the PI in a secure storage facility. The records will be accessible for inspection and copying by authorized authorities. Hardcopy study documents will be kept under lock and key in the PI's office, and softcopy data will be kept in a password protected file, with patient identifiers stored separately, and access limited only to the study team. These study documents and data will be kept for a minimum of 6 years after completion of the study.

## **List of Attachments**

**Appendix 1      Chest Pain Choice Visual Aid**

**Appendix 2      Questionnaires used in the Trial**

**Appendix 3      Sample Patient Information Sheet and Informed Consent Form**
